7.4.4 Analyses of Endpoints for the Optional Substudy

All analyses will use the approaches outlined in Section 7.4.1.1 for the primary analyses, in Section 7.4.2 for the key secondary analyses and those outlined in Section 7.4.3.1 for secondary analyses.

The number and percentage of subjects without colonization at either Day 92 or Day 99 will be calculated by treatment group (BPZE1, BPZE + Boostrix, BPZE1 and BPZE1 + Boostrix, Boostrix control). The number and percentage of subjects without colonization at Day 92 and Day 99 will also be calculated by treatment group (see Section 7.4.2 for a description of the approach).

BPZE1, BPZE1 + Boostrix, BPZE1 and BPZE1 + Boostrix, and Boostrix control of induction of mucosal S-IgA at Day 29 and Day 85 will be summarized and compared by protection against colonization (Colonizers/Non-colonizers) using a two-sample t-test.

BPZE1 induction of mucosal S-IgA immunity at Day 113 will be compared with that at Day 29 and Day 85 (by treatment group) using a paired t-test to assess if a re-vaccination/attenuated challenge with BPZE1 provides significantly more mucosal S-IgA induction by treatment group (BPZE1, BPZE1 + Boostrix). To demonstrate that BPZE1 following Boostrix provides a similar level of induction as BPZE1 alone, a two-sample t-test will be used to test for the difference of mucosal S-IgA immunity at Day 113 (Boostrix versus BPZE1).

BPZE1, BPZE1 + Boostrix, or control (Boostrix) induction of mucosal S-IgA at Day 113 and Day 169/EOS will be summarized and compared using a two-sample t-test between subjects who participated in the substudy and subjects who did not participate in the substudy by treatment group.

Bordetella pertussis colony counts at each of Day 92 and Day 99 (individual and total) will be summarized descriptively and the Wilcoxon Rank-Sum test will be used to compare colony counts. Mean counts and AUC will be calculated across Day 92 and Day 99. Colonization versus non-colonization status for Day 92, Day 99, and for the combined result over Day 92 and Day 99 will be tabulated.

To assess if prior BPZE1 induced mucosal immunity substantially reduces colonization at Day 92 and Day 99, the number and percentage of subjects with colonization at each of Day 92 and Day 99 will be analysed based on mucosal S-IgA at Day 29 and Day 85 (see Section 7.4.2 for analysis approach). The percent reduction (with 95% CI) relative to the Boostrix control group at each of Day 92 and Day 99 will be summarized.

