5.2 Treatments Administered

Subjects in Treatment Group A (N ~120) will receive an intranasal application of 10^9 CFU BPZE1, with approximately 0.4 mL per nostril (0.8 mL total volume delivered); and an IM injection of 0.5 mL placebo (sterile normal saline for injection) to the deltoid region on Day 1. Intranasal application of BPZE1 or placebo should precede IM injection of Boostrix or placebo by at least 10 minutes (minimum of 30 minutes for subjects in the safety lead-in cohort of 11 to 17 year olds). For the safety lead-in cohort, a minimum of 30 minutes must occur between intranasal and IM vaccinations on Day 1.

Subjects in Treatment Group B (N ~120) will receive an intranasal application of 10^9 CFU BPZE1, with approximately 0.4 mL per nostril (0.8 mL total volume delivered); and an IM injection of 0.5 mL Boostrix (aP vaccine, manufactured by GlaxoSmithKline) to the deltoid region on Day 1. Intranasal application of BPZE1 or placebo should precede IM injection of Boostrix or placebo by at least 10 minutes (minimum of 30 minutes for subjects in the safety lead-in cohort of 11 to 17 year olds).

Subjects in Treatment Group C (N ~120) will receive an intranasal application of lyophilized buffer reconstituted in sterile water, with approximately 0.4 mL per nostril (0.8 mL total volume delivered); and an IM injection of 0.5 mL Boostrix (aP vaccine, manufactured by GlaxoSmithKline) to the deltoid region on Day 1. Intranasal application of BPZE1 or placebo should precede IM injection of Boostrix or placebo by at least 10 minutes (minimum of 30 minutes for subjects in the safety lead-in cohort of 11 to 17 year olds).

All subjects participating in the optional substudy will receive a second intranasal application of 10^9 CFU BPZE1, with approximately 0.4 mL per nostril (0.8 mL total volume delivered) on Day 85.

All subjects will be monitored for study vaccination-related events for at least 30 minutes following the last vaccination (eg, 30 minutes following IM vaccination).

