- ^c Subjects not participating in the substudy are to complete procedures listed under Study Visit V3 for Day 85. Subjects in the safety lead-in cohort who are not participating in the substudy are not required to provide samples on Day 85 and may complete this visit remotely.
- ^d Subjects participating in the substudy (only) to complete procedures listed under Study Visits SSV3, SSV4, SSV5, and SSV6.
- ^e Procedures listed for an Unscheduled study visit are optional and dependent on the cause for the visit itself. An unscheduled study visit may occur at any time between enrolment and Day 169/EOS.
- ^f Reviewed and/or updated.
- ^g Performed prior to vaccination.
- ^h Such as date of birth (where allowed by local regulations), sex, race, ethnicity, weight, and height (with derived BMI and Z-score).
- ⁱ Including prior and ongoing chronic medical conditions and past surgeries.
- ^j Concomitant medications will include all medications and OTC products (including herbal supplements and multivitamins) taken by the subject from the time of signing the ICF through Day 29 (and from Day 85 [following study vaccination] through Day 113 for subjects participating in the optional substudy), or through an early termination visit, if prior to these time points. The use of anti-pyrogenic medication will be specifically queried by diary during the 7 days following any study vaccination.
- ^k Only concomitant medications associated with any MAAE (through 84 days following any study vaccination); or AESI or SAE (through Day 169/EOS) will be recorded.
- ^l Vaccines received outside of the study will be specifically queried during each visit and recorded through Day 169/EOS.
- ^m Targeted physical examination at screening and Day 1 (prior to vaccination) to include head and neck (inclusive of nasal cavity and oropharynx), respiratory, cardiac, abdomen, and lymph nodes associated with the upper extremity, head, and neck. Targeted physical examination at all other times will be symptom-directed and performed at the discretion of the investigator. Height and weight will be measured at screening only.

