8.4.2. Analysis of Mucosal Secretory Immunogenicity Endpoints

BPZE1, BPZE1 + Boostrix, BPZE1 and BPZE1 + Boostrix, and Boostrix control induction of mucosal S-IgA at Days 29 and 85 will be summarized by protection against colonization (Colonizers/Non-colonizers) and by treatment group and by timepoint. Separate two-sample t-tests will be used to compare the natural log-transformed GMRs at Days 29 and 85 between Colonizers and Non-colonizers by treatment group and by timepoint.

To test the hypothesis that BPZE1 and BPZE1 + Boostrix can induce mucosal S-IgA at Day 113 compared with Day 85, separate paired t-tests will be used to compare the natural log-transformed GMCs/GMRs at Day 113 with the natural log-transformed GMCs/GMRs at Day 85 within each treatment group. The corresponding 95% CIs will be calculated on the natural log scale, then both lower and upper limits will be exponentiated to get the 95% CIs on the original scale.

BPZE1, BPZE1 + Boostrix, or Boostrix control induction of mucosal S-IgA at Day 113 and Day 169/EOS will be summarized by participation in the substudy (Yes/No) and by treatment group and by timepoint. Separate ANCOVA models that include baseline S-IgA and an indicator of participation in the substudy (Yes/No) as covariates will be used to compare between subjects who participated in the substudy and subjects who did not participate in the substudy, by treatment group and by timepoint.

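### The Day 113 Boostrix-versus-BPZE1 S-IgA test compares one BPZE1 dose with two, so it does not isolate the effect of prior Boostrix that it is meant to assess

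*Protocol*

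**What the plan says.** Protocol 7.4.4 gives the aim and the method in one sentence: "To demonstrate that BPZE1 following Boostrix provides a similar level of induction as BPZE1 alone, a two-sample t-test will be used", the test being one to "test for the difference of mucosal S-IgA immunity at Day 113 (Boostrix versus BPZE1").

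Protocol 5.2 fixes who has received BPZE1 by then.

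- BPZE1 group, Day 1: "Subjects in Treatment Group A (N ~120) will receive an intranasal application of 10^9 CFU BPZE1", with intramuscular placebo.
- Boostrix group, Day 1: "Subjects in Treatment Group C (N ~120) will receive an intranasal application of lyophilized buffer reconstituted in sterile water", with intramuscular Boostrix.
- Substudy, Day 85, whatever the Day 1 group: "All subjects participating in the optional substudy will receive a second intranasal application of 10^9 CFU BPZE1".

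Day 113 is visit SSV6, and the schedule in Protocol 13.1 restricts it: "Subjects participating in the substudy (only) to complete procedures listed under Study Visits SSV3, SSV4, SSV5, and SSV6".

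SAP 8.4.2 has no between-group test at Day 113. Its Day 113 test by randomised group is within group: "To test the hypothesis that BPZE1 and BPZE1 + Boostrix can induce mucosal S-IgA at Day 113 compared with Day 85". It also plans a comparison of substudy participants with non-participants. The BPZE1-versus-Boostrix ANCOVA on S-IgA in SAP 8.3.1 covers Days 29, 85 and 169/EOS. SAP Section 1 gives the SAP precedence where it is inconsistent with the protocol. SAP Section 11 records one change, the added 10 to 17 year age group.

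**The concern.** The purpose named in Protocol 7.4.4 needs two groups that differ in prior Boostrix and are otherwise alike in BPZE1 exposure. At Day 113 no such pair exists. Every sampled BPZE1-group subject has been dosed twice, and no arm has had a single BPZE1 dose without Boostrix, so no covariate adjustment at Day 113 recovers the intended contrast.

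The protocol does not treat the second dose as neutral. The sentence just before this one tests whether re-vaccination raises S-IgA further. The substudy's exploratory colonization objective is that prior BPZE1 reduces colonization after the Day 85 dose, so that dose may act differently in the two groups.

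At stake is how a reported result would be read. A lower value in the Boostrix group could reflect one dose against two and say nothing about prior Boostrix. Equal values could hide two effects that offset each other.

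**Working it through.** **1. Dose count and timing at Day 113** (nominal days, Protocol 5.2 and 13.1)

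| Group | BPZE1 doses | Days since first BPZE1 | Days since latest BPZE1 |
|---|---|---|---|
| BPZE1 | 2 (Days 1, 85) | 113 - 1 = 112 | 113 - 85 = 28 |
| Boostrix | 1 (Day 85) | 113 - 85 = 28 | 28 |

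The BPZE1 + Boostrix group has also had two doses.

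**2. What the contrast estimates**

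On the natural log scale, let p be the effect of prior Boostrix on the response to a first BPZE1 dose, and k the net effect at Day 113 of having had an extra, earlier BPZE1 dose. Then

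expected difference (Boostrix minus BPZE1) = p - k.

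The data give p - k only. It equals p if k = 0. If p = 0 and the net boost is 1.5-fold, the expected difference is -ln 1.5 = -0.405, although prior Boostrix did nothing. If p = k, the expected difference is zero whatever their common size.

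**3. Illustration of size**

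The documents give no sample size, power or S-IgA SD for this test. As a check on the method, the plan's one S-IgA design figure reproduces: paired t-test, n = 108, effect size 0.35, two-sided 0.05, noncentrality 0.35 x sqrt(108) = 3.64, power 0.950 against the stated 95%.

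Inputs for the illustration:

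- n = 40 per group: the substudy maximum of 120 (Protocol 3.1.1) divided by 3. The even split is an assumption.
- ln SD 0.8, 1.0 and 1.4: assumed. The range resembles the serum IgG SDs in SAP Table 4-2, which are not S-IgA values.
- Limit -0.693: from Protocol 7.4.2. The sentence at issue does not name it.
- p = 0, and a net boost of fold b, so k = ln b.

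Standard error = SD x sqrt(2/40); at SD 1.0 this is 0.2236. Noncentrality = (0.693 - ln b) / SE. The chance that the lower 95% limit exceeds -0.693 is the probability that a noncentral t with 78 df exceeds 1.991.

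- b = 1: 0.693 / 0.2236 = 3.10, giving 0.86.
- b = 1.5: (0.693 - 0.405) / 0.2236 = 1.29, giving 0.25.

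| ln SD | b = 1 | b = 1.25 | b = 1.5 | b = 2 |
|---|---|---|---|---|
| 0.8 | 0.97 | 0.74 | 0.36 | 0.03 |
| 1.0 | 0.86 | 0.55 | 0.25 | 0.03 |
| 1.4 | 0.59 | 0.32 | 0.15 | 0.03 |

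The normal approximation agrees within about 0.01. In every cell prior Boostrix has no effect; the fall across a row comes from the unequal number of doses alone.

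**4. A dose-matched pair already in the schedule**

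Boostrix group, Day 85 (pre-dose) to Day 113: 28 days after its first BPZE1 dose. BPZE1 group, Day 1 (pre-dose) to Day 29: 29 - 1 = 28 days after its first. Nasal immunogenicity sampling is scheduled at all four points.

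**The case against.** The strongest reply is that the test will probably not be run. The SAP governs, its substudy section omits the test, and its BPZE1-versus-Boostrix S-IgA model stops short of Day 113. The aim appears in a single sentence of Protocol 7.4.4 and matches no listed objective or endpoint. The substudy is open-label and opt-in, and Protocol 5.1 already accepts some bias from that. This stands and sets the priority. It does not settle the matter, because the SAP is silent on the test and Section 11 does not record its removal. A reader cannot tell whether the protocol test survives or was dropped.

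A second reply is that the protocol expects boosting not to be needed (Section 1.2), and that one dose appeared sufficient in adults (Section 1.1). If the extra dose has no net effect at Day 113, the contrast is valid; if it boosts, the bias runs against claiming similarity. This is fair, so it would be too strong to say that the test can never answer its question. But the protocol leaves the size of the boost open.

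A reader might also infer that a non-significant t-test will be reported as similarity. With 40 per group, power against a true 1.5-fold gap would be 61%, 43% and 25% at ln SD 0.8, 1.0 and 1.4. The documents do not state that decision rule. Section 7.4.4 opens by adopting the approaches of 7.4.2 and 7.4.3.1, where a two-sample t-test for non-inferiority goes with the -0.693 limit. What can be said is that this sentence names no margin. Those power figures depend on the inferred rule and do not measure the dose imbalance.

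**Conclusion.** The point holds in a limited form. As worded, the Day 113 test compares two BPZE1 doses with one BPZE1 dose after Boostrix. It estimates the effect of prior Boostrix only if the net effect of the extra dose is zero. The dose count follows directly from the protocol and needs no assumption. The size of any distortion is unknown; the fall from about 0.86 to about 0.25 rests on an assumed 40 per group, an assumed ln SD of 1.0, an assumed 1.5-fold boost and use of the -0.693 limit.

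A reader might infer that a substudy objective is left without a valid analysis. The documents do not support that: the listed substudy S-IgA objectives concern the relation to colonization, the change from Day 85 to Day 113, and participants against non-participants. The primary, key secondary and listed substudy endpoints are unaffected. This is a low-priority correction.

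**What to change.** Amend Protocol 7.4.4 and SAP 8.4.2 together, in one of two ways.

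- **Minimum.** Delete the test and record the removal in SAP Section 11.
- **If the question is to be kept.** Label the Day 113 contrast 'two BPZE1 doses versus one BPZE1 dose after Boostrix'. For the stated aim, add an exploratory comparison of the Boostrix group's ln rise from Day 85 to Day 113 with the BPZE1 group's ln rise from Day 1 to Day 29, adjusted for pre-dose S-IgA and age. Report the ratio with its 95% CI against the plan's -0.693 limit. Use all BPZE1-group subjects with Day 29 data, with substudy participants only as a sensitivity analysis.

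The cost is wording and programming; no new sample or visit is needed. The replacement is not a clean randomised comparison, and the report should say so: the two rises fall in different calendar periods, one dose is open-label and the other blinded, the Boostrix-group subjects chose to take part, and their pre-dose value is measured after Boostrix.

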7.4.5 Other Analyses

Summary statistics will be provided for exploratory endpoints, demographic and baseline data, medical history, vital sign measurements, physical examination, study vaccination compliance, and prior and concomitant medications.

Cellular immune response (Th1 and Th2) following study vaccination will be evaluated in the safety lead-in analysis set using baseline and Day 8 and in the substudy using Day 85 and Day 113 (subset). Parameters will be summarized using descriptive statistics and a formal test of differences in Th1 vs Th2 pathway induction between treatment groups. The 95% CI of median will be provided. Median of fold rise over baseline will also be provided.

If a substantial number of subjects receive a COVID-19 vaccine that is under an emergency use authorization only, then safety analysis may also assess any AEs that may be confounded by such concomitant vaccine administration during the study.

7.4.6 Interim Database Lock

An interim database lock may occur after all subjects have completed Day 29 and sample testing for all primary and select secondary immune endpoints has been completed (mucosal and serum), but results will only be provided at treatment assignment level to maintain the blind. The site and those interacting directly with the site or subject data (eg, CRO, laboratories) will remain blinded to subject assignment until EOS or end of sample testing, depending on the activities of the associated entities.

8 Data Quality Assurance

The sponsor will perform quality control and assurance checks on all clinical studies that it sponsors. Before enrolling any subjects in this study, sponsor personnel and the investigator will review the protocol, the package inserts, investigator brochures, the eCRFs and instructions for their completion, the procedure for obtaining informed consent, and the procedure for reporting AEs and SAEs. A qualified representative of the sponsor will monitor the conduct of the study by visiting the site and by contacting the site by telephone and e-mail. During these site visits, information recorded in the eCRFs will be verified against source documents.

8.1 Data Management

As part of the responsibilities assumed by participating in the study, the investigator agrees to maintain adequate case histories for the subjects treated as part of the research under this protocol. The investigator agrees to maintain accurate eCRFs and source documentation as part of the case histories. These source documents may include subject diaries for reactogenicity reporting.

Investigative site staff will enter subject data into an approved and auditable data management system. The analysis data sets will be a combination of these data and data from other sources (eg, laboratory data).

Clinical data management will be performed in accordance with applicable CRO and/or sponsor standards and data cleaning procedures to ensure the integrity of the data (eg, removing errors and inconsistencies in the data). Adverse event terms (including SAEs) will be coded using MedDRA, an internal validated medical dictionary, and concomitant medications will be coded using the WHO Drug Dictionary.

9 Ethics

9.1 Independent Ethics Committee

Federal regulations and the International Council for Harmonisation (ICH) guidelines require that approval be obtained from an independent ethics committee (IEC) before participation of human subjects in research studies. Before study onset, the protocol, informed consent, advertisements to be used for the recruitment of study subjects, and any other written information regarding this study to be provided to the subject or the subject's legal guardian must be approved by the IEC. Documentation of all IEC approvals and of the IEC compliance with ICH harmonised tripartite guideline E6 (current version): Good Clinical Practice (GCP) will be maintained by the site and will be available for review by the sponsor or its designee.

All IEC approvals should be signed by the IEC chairman or designee and must identify the IEC name and address, the clinical protocol by title or protocol number or both, and the date approval or a favourable opinion was granted.

The investigator is responsible for providing written summaries of the progress and status of the study at intervals not exceeding 1 year or otherwise specified by the IEC. The investigator must promptly supply the sponsor or its designee, the IEC, and, where applicable, the institution, with written reports on any changes significantly affecting the conduct of the study or increasing the risk to subjects.

9.2 Ethical Conduct of the Study

The study will be performed in accordance with the ethical principles that have their origin in the Declaration of Helsinki, ICH GCP, the protocol, and all applicable regulations.

9.3 Subject Information and Consent

A written informed consent (and assent, if applicable) in compliance with regulatory authority regulations shall be obtained from each subject and/or his or her legal guardian before entering the study or performing any unusual or nonroutine procedure that involves risk to the subject. An ICF and subject information sheet/authorization form template may be provided by the sponsor to investigative sites. If any institution-specific modifications to study-related procedures are proposed or made by the site, the ICF and subject information

sheet/authorization form should be reviewed by the sponsor or its designee or both before IEC submission. Once reviewed, the ICF and subject information sheet/authorization form will be submitted by the investigator to his or her IEC for review and approval before the start of the study. If the ICF or subject information sheet/authorization form is revised during the course of the study, all active participating subjects and or legal guardians must sign the revised form(s). A separate ICF will be utilized for subjects participating in the substudy.

Before recruitment and enrolment, each prospective subject and/or his or her legal guardian will be given a full explanation of the study, be allowed to read the approved ICF (or subject information sheet/authorization form, if applicable), and have any questions answered. Once the investigator is assured that the subject/legal guardian understands the implications of participating in the study, the subject/legal guardian will be asked to give consent (and assent, if applicable) to participate in the study by signing the ICF (and subject authorization form, if applicable). The authorized person obtaining the informed consent also signs the ICF (and subject authorization form, if applicable).

The ICF and subject information sheet/authorization form will contain separate sections that address the use of remaining mandatory samples for optional exploratory research (if applicable) and explain/address the exploratory research portion of the study. Subject medical records need to state that written informed consent was obtained.

The investigator shall retain the signed original ICF(s) (and subject authorization form[s], if applicable) and give copies of the signed original form(s) to the subject and/or legal guardian.

10 Investigator's Obligations

The following administrative items are meant to guide the investigator in the conduct of the study but may be subject to change based on industry and government standard operating procedures, working practice documents, or guidelines. Changes will be reported to the IEC but will not result in protocol amendments.

